4.4. Criteria for Study Termination

BPL reserves the right to terminate the study or a clinical study site at any time (see [Section 12.11](#) for details). Conditions that may warrant termination of the study include, but are not limited to

- The discovery of an unexpected, serious, or unacceptable risk to patients enrolled in the study
- The decision on the part of BPL to suspend or discontinue testing or the treatment with the study drug
- Failure of the Investigator to comply with Good Clinical Practice (GCP)
- Submission of knowingly false information from the clinical study site to BPL or designee or to regulatory authorities
- Insufficient adherence to protocol requirements

If terminating the study, BPL or designee and the Investigator(s) will ensure that adequate consideration is given to the protection of patients' interests.

4.5. Risk Mitigation

The design of this Phase 2a study is based on the European Medicines Agency Guideline on strategies to identify and mitigate risks for early clinical studies with IMPs ([European Medicines Agency, 2017](#)).

This study has been designed to mitigate the known risks associated with classic psychedelics and the 5-HT_{2A} receptor agonist class, and the potential risks based on nonclinical toxicity data, epidemiological studies of the use of 5-MeO-DMT for spiritual/recreational purposes, and safety data obtained from studies of 5-MeO-DMT in healthy volunteers. The key risk mitigation plans include definition of the patient population via the eligibility criteria; adherence to the guidelines for the safe use of psychedelics ([Johnson, 2008](#)), with particular attention paid to the set and setting parameters; observation of participants for 24 hours following drug administration; and provision of psychological support during and after the study.

Additional safety risk to study participants is mitigated by the following considerations:

- The available clinical and preclinical toxicity data indicate an acceptable safety profile for BPL-003. For a full list of studies, please refer to the current version of the IB.
- The doses selected for this study have been evaluated in a Phase 1 study with healthy volunteers (BPL-003-103).
- Concomitant medications with known or suspected PK or PD interactions with 5-MeO-DMT have been excluded; notably MAO-Is are prohibited.
- Patients must have a breath alcohol level of zero prior to dosing.
- The psychedelic experience may result in adverse psychological reactions, such as increased levels of anxiety, hallucinations, or flashbacks. The Investigator and therapists will provide psychological support throughout the study to manage any adverse psychological reactions. This will be done through the preparatory visits, during dosing, and the integration visits. Furthermore, only those persons with disposition judged by the Investigator to be compatible with establishment of rapport with study team and/or safe exposure to BPL-003 will be included in the study.
- Patients will be briefed on what to expect during BPL-003 dosing through preparatory meetings and familiarised with the dosing procedure and setting, as recommended by published guidelines ([Johnson, 2008](#)).
- Patients will receive the dose and spend their dosing experience in a safe, comfortable, and relaxing physical session environment.
- A physician must be present in the room for the 90 minutes immediately after drug administration in order to closely observe each patient.
- Vital signs including temperature will be measured after dosing.
- The clinic is experienced with trials of psychedelic compounds similar to BPL-003 and will follow its standard operating procedures (SOPs).

- The study site will be suitably prepared to deal with any medical emergencies. A medical emergency is an acute, unplanned event that has the potential for serious harm or death, including anaphylaxis and cardiorespiratory arrest. Resuscitation trolleys are to be located in nearby areas. Trolleys are to be checked on a regular basis to ensure that all drugs and equipment are in-date and functional. Study site staff will be suitably trained and an appropriate number of trained staff will be with the patients during and after dosing to ensure any emergencies can be dealt with safely.
- For safeguarding purposes, the dosing session will be video recorded, and all preparation sessions and integration sessions will be audio only recorded. These recordings will only be reviewed on an ad-hoc basis for safety and adherence purposes. In addition, subject to specific consent by participants, the audio and video recording of the sessions may be used for other purposes. These are for therapy optimisation, with the purpose of improving further training manuals and procedures, or for Sponsor (or delegate) training purposes. Additional consent will be sought for these activities. Participants who do not consent to the use of recordings for therapy optimisation or training purposes will not be excluded from the study. The audio and video recordings will be stored securely with restricted access, in compliance with UK data protection law (including General Data Protection Regulation or GDPR). Benzodiazepines, including oromucosal midazolam, and other suitable tranquilising treatment will be available as a rescue medication, if needed.

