- **Psychedelic preparation visits:** Following the initial Screening Visit, all patients will participate in 3 preparatory sessions over approximately 2 weeks before being dosed (patients should not undertake preparation sessions if intoxicated (clinical judgement to be applied whether the patient is able to absorb the information and build a therapeutic alliance). The aim will be to establish a therapeutic alliance with the therapists during the preparatory sessions so that patients will be well prepared for the BPL-003 treatment session and receive ongoing AUD relapse prevention psychotherapy.
- **Psychological change measures and semi-structured interviews (optional):** if patients consent to these optional assessments they will be required to complete psychological change questionnaires at 5 visits during the study on Days -3, 1, 7, 28 and 84, and 3 semi-structured interviews with a therapist on Days 1, 28 and 84 (as detailed in the Psychological Change Study Manual).
- **Dosing visit:** After completion of the 3 preparatory sessions, patients will attend the clinic for their dosing visit. Patients will be resident at the clinic from the morning of Day 0 (dosing day) until at least 4 hours postdose. BPL-003 will be administered to patients in the designated setting, and the therapist will remain with patients while patients are in an altered state of consciousness.

- **Qualitative interview (optional):** After return to a usual state of consciousness after dosing, and provided they consent, patients will be asked to have a one-to-one guided qualitative interview with independent researchers trained in microphenomenology methods to discuss their psychedelic experience (as detailed in the Qualitative Interview Study Manual). This will be done either face to face at the clinic or via video call. Psychometric scales will then be administered to provide quantitative measures of the patient's psychedelic experience. All patients will have their readiness for discharge assessed every 30 minutes starting 90 minutes after dosing before discharge on the dosing day. The earliest a patient can be discharged will be 4 h after receiving the dose.
- **Follow-up (for 12 weeks postdose):**
 - **Psychedelic integration sessions:** Patients will have at least 3 integration sessions, lasting approximately 60-90 min, over the 2 weeks following their dose to discuss their experience with the therapists.

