1.6. Risk-Benefit Profile

Steps taken to mitigate risk in the present study are described in [Section 4.5](#).

Potential Risks:

- Adverse events related to the serotonergic system, including tachycardia and raised blood pressure
- Adverse events during the psychedelic experience, including anxiety, confusion, paranoia, and dissociation
- Psychological adverse events following the psychedelic experience
- Nasal and/or pharyngeal irritation postdose

Potential Benefits:

Alleviation of the symptoms of addiction following administration of 5-MeO-DMT has been reported anecdotally and in epidemiological studies.

The overall risk-benefit ratio is considered acceptable.

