6.6. Study Visits

The study visits are outlined below. Study visits and procedures are also detailed in the Schedule of Events in [Table 1](#).

- **Screening:** Patients will be screened up to 14 days before their psychedelic preparation session to confirm their eligibility for the study.
- **Abstinence:** Patients will be expected to have no HDD at least 72 hours prior to dosing and no alcohol at all in the 24 hours prior to dosing. If breath alcohol is not zero on dosing day, patients may reschedule once if they are deemed not to have completely relapsed; however, if they fail the second time, they will be excluded from the study.
- **Psychedelic Preparation Sessions:** Following the initial Screening Visit, all patients will participate in 3 preparatory sessions over approximately 2 weeks before being dosed (patients should not undertake preparation sessions if intoxicated, as recommended by published guidance on the conduct of studies of psychedelic compounds) ([Johnson, 2008](#)). Investigator discretion to be applied where patient has some alcohol in their system, but is still able to absorb the information and build a therapeutic alliance. The aim will be to establish a therapeutic alliance during the preparatory sessions so that patients will be well prepared for the BPL-003 treatment session and receive ongoing AUD relapse prevention psychotherapy. The psychedelic preparation session will be audio recorded for safety and quality assurance purposes.
- **Dosing Visit:** After completion of the 3 preparatory sessions, patients will attend the clinical study facility for their dosing visit. Patients will be resident at the clinic from the morning of Day 0 (dosing day) until approximately 4 hours postdose.
 - BPL-003 will be administered to patients in the designated setting, in accordance with published guidelines for clinical trials of psychedelic compounds ([Johnson, Richards and Griffiths, 2008](#)), with particular emphasis on 'set' (the subject's mental state prior to dosing) and 'setting' (the dosing environment). The psychedelic therapist will remain with patients while patients are in an altered state of consciousness.

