 - During the dosing session, the therapist will be supportive and non-directive, and not attempt to influence the patient's psychedelic experience. Site staff will be trained to maximise patients' psychological welfare during dosing and the subsequent psychedelic experience (e.g., assessments will be performed with as minimal interruption as possible;

patients will be encouraged to lie down during dosing). All psychological support providers will be trained in accordance with the therapy manual.

- All dosing sessions will be audio/video recorded for safety and quality assurance purposes
- After return to a usual state of consciousness after dosing, patients will be asked to have a one-to-one guided qualitative interview with independent researchers trained in microphenomenology methods to discuss their psychedelic experience (as detailed in the Qualitative Interview Study Manual). This will be done either face to face at the clinic or via video call. Clinical research measures will then be administered to provide quantitative measures of the patient's psychedelic experience.
- After dosing, the patients will have to remain at site for at least 4 h. Patients may be discharged 4 h after dosing, provided the Investigator or psychiatrist determines that it is safe for the patient to leave, having assessed their individual psychological wellbeing. All patients will have their "readiness for discharge" (see Appendix) assessed every 30 min starting 90 min after dosing. If the patient is not ready for discharge at 4 h post dose, then the questionnaire will be repeated when the Investigator believes the patient may be ready for discharge.
- If the study team considers that a patient may pose a risk to themselves or others, they may be prevented from leaving the site. Patients will be informed of that possibility, and consent to it, at Screening. Any actions taken to minimise a participant's risk to themselves or others and/or prevent them from leaving the site will be undertaken in accordance with appropriate legislation.

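### Protocol Section 4.5 lists 24 hours of observation after dosing as a key safeguard, but the dosing-day rules in the protocol and SAP allow conditional release from 4 hours; the passages need reconciling

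*Protocol*

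**What the plan says.** Protocol Section 4.5 names a short set of key risk-mitigation plans: the eligibility criteria, adherence to published guidance on safe psychedelic use, "observation of participants for 24 hours following drug administration", and psychological support during and after the study. Section 1.6 opens with "Steps taken to mitigate risk in the present study are described in" Section 4.5 and, after listing potential risks and benefits, ends with "The overall risk-benefit ratio is considered acceptable".

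The passages that govern the dosing day describe a shorter stay:

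- Protocol synopsis: "The earliest a patient can be discharged will be 4 h after receiving the dose". SAP Section 5 repeats this rule.
- Protocol Section 6.6, Dosing Visit: the patient is resident "from the morning of Day 0 (dosing day) until approximately 4 hours postdose". Later in the same section: "After dosing, the patients will have to remain at site for at least 4 h", with discharge then allowed "provided the Investigator or psychiatrist determines that it is safe for the patient to leave".
- Protocol Table 1, footnotes 4 and 10: vital signs and readiness checks run to 4 hours, and are repeated at discharge if that is later.
- Protocol Section 9.15 and Appendix 2: a patient found ready early still stays until 4 hours; a patient not ready at 4 hours is reassessed later.

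Section 6.7 deals with the patient after release. A responsible adult should accompany them, and driving and machine work are barred for 24 hours after dosing.

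**The concern.** The risk-mitigation section is where a reader looks for the safeguards, and Section 1.6 sends the reader there before it judges the risk-benefit ratio. One of the few measures singled out as key is a specific duration that the visit plan does not provide. The primary objective is safety and tolerability, and Section 4.3 says this is the first study of BPL-003 in this population. The stated safety provisions should therefore be ones the design contains. As the text stands, a reader of Sections 1.6 and 4.5 and a reader of Section 6.6 come away with different accounts of what happens to a patient between 4 and 24 hours after the dose.

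**Working it through.** The plan gives no derived figure to reproduce. The check sets the stated 24 hours beside each provision that covers the first day.

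| Provision | Where stated | Time covered after dosing |
|---|---|---|
| Observation, as a key risk mitigation | Protocol 4.5 | 24 h |
| Physician in the room | Protocol 4.5 | 90 min |
| Cardiac telemetry | Protocol 10.1.6; Table 1 footnote 23 | 90 min |
| Scheduled vital signs | Protocol Table 1 footnote 4 | to 4 h, or discharge if later |
| Readiness checks | Protocol Table 1 footnote 10; 9.15; Appendix 2 | from 90 min to 4 h, repeated later if not ready |
| Minimum stay on site | Protocol synopsis, 6.6, 9.15, Appendix 2; SAP 5 | 4 h |
| Next scheduled visit | Protocol Table 1; Table 4 | Day 1, plus or minus 2 days |

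**Step 1: the gap.** Stated observation minus guaranteed stay: 24 − 4 = 20 h. As a share of the stated period, 20/24 = 83%; the guaranteed part is 4/24 = 17%. The 20 hours apply to a patient released at exactly 4 hours. Anyone kept longer has a smaller gap.

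**Step 2: can the Day 1 visit supply the 24-hour check?** Table 1 footnote 2 says Day 1 may not be done remotely, and Table 1 schedules vital signs, an ECG, laboratory tests, the C-SSRS and adverse events there. Table 4 accepts plus or minus 2 days for this visit without a deviation, so it may fall as late as Day 1 + 2 = Day 3. A visit on Day 3 meets the schedule but is not a check at 24 hours, and a single later visit is not observation over 24 hours.

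**Step 3: does any passage provide for the interval?** Table 1 has no column between Day 0 and Day 1. Section 6.7 assumes the patient has left within 24 hours, since it sets conditions for release and restricts activity for the rest of that period. It assigns no observation to site staff and does not describe the accompanying adult as an observer. Section 4.5 does not define observation.

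**Step 4: the 4-hour wording.** The Dosing Visit text in Section 6.6 says "until approximately 4 hours postdose", which taken literally allows slightly less than 4 hours. The later text in that section and the synopsis make 4 hours a floor.

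**The case against.** The strongest reply is that site practice is not in doubt. All the operational passages and the SAP agree on a 4-hour minimum; one general sentence in Section 4.5 differs. The minimum is also conditional: Appendix 2 requires every readiness item to be answered yes, the investigator or psychiatrist must judge release safe, and Section 6.6 lets the site keep a patient longer. Observation is undefined, so the accompanying adult, the 24-hour activity restriction and the in-person Day 1 visit might be what Section 4.5 had in mind. Section 1.4.2.3.1 adds that, in healthy volunteers, mean half-lives ranged from 15 to 27 minutes and most probably related events lasted from minutes to 1–2 hours.

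Much of this stands. It limits the point to an inconsistency of text and means the 83% cannot be read as a share of risk. It does not supply the 24 hours: no passage assigns observation between release and Day 1, and the Day 1 window does not secure a check at 24 hours.

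A reader might go further and infer three things that the documents do not support:

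- *That the primary safety endpoint is compromised by two kinds of event ascertainment.* Section 10.2.4 sets one method for the whole study, with non-leading questioning that also covers the time since the previous visit. The study is single-arm and descriptive with no hypotheses (Sections 6.5 and 11.1), so no endpoint bias is shown.
- *That the risk-benefit conclusion depends on the 24 hours.* Section 1.6 only cross-refers to Section 4.5, which lists many other measures.
- *That the ethics committee relied on the 24-hour statement.* Nothing in the documents shows this, and the 4-hour rule appears openly in the same protocol.

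**Conclusion.** The inconsistency is real and is in the current text. Section 4.5 states a 24-hour safeguard; the synopsis, Table 1 footnotes, Section 6.6, Section 9.15, Appendix 2 and SAP Section 5 provide a conditional 4-hour minimum. At most 20 of the 24 stated hours have no observation specified. That figure assumes release at exactly 4 hours and takes observation to mean something the protocol assigns to the site.

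This should be fixed as an internal inconsistency. No endpoint, population or analysis changes because of it. It would also be wrong to conclude that 24 hours is the correct standard and the schedule falls short of it: the documents show only that the passages conflict, and choosing the period is a clinical decision for the sponsor and investigators.

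**What to change.** 1. Reconcile Section 4.5 with the synopsis, Table 1 footnotes 4 and 10, Section 6.6, Section 9.15, Appendix 2 and SAP Section 5, so that one post-dose observation period is stated throughout.
2. If any part of that period falls after release, say what observation then means: who does it, how, and how it relates to the Day 1 visit and its window.
3. Within Section 6.6, make the two statements of the 4-hour stay agree.
4. Re-confirm the Section 1.6 risk-benefit statement against the reconciled Section 4.5.

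The cost is protocol and SAP wording, plus clinical and ethics confirmation of the reconciled period. If the sponsor's decision leaves the dosing-day schedule as it is, nothing changes in data collection. If it alters the schedule, the operational cost is larger. No change to the adverse-event tables is needed for this point.

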4.5.1. COVID-19

The Investigator and BPL have reviewed the risks of conducting the study in light of the current COVID-19 pandemic. The first priority is the safety of study patients and staff; however, the Investigator and BPL also have an ethical duty to preserve the scientific integrity of the study as far as possible.

Exposure to BPL-003 is unlikely to increase the risk of contracting COVID-19 infection or to worsen the severity of an infection.

There is no interaction with BPL-003 that might affect any aspect of vaccination, such as timing or efficacy. However, to enable a clearer determination of relationship between BPL-003 and any adverse events, it would be advisable, where possible, for the vaccination to be given 7 days before or 7 days after the single dose of BPL-003.

The study will be run at two sites, Clerkenwell Health and the NIHR Wellcome King's Clinical Research Facility which fall under the King's College Hospital NHS Trust and the Lorraine Hewitt House which falls under the South London and Maudsley NHS Trust, in collaboration with King's Health Partners. To keep patients and site staff safe, the study will be run in line with the Trust's policies for managing studies during the pandemic. This includes strict infection prevention control measures, such as reducing site traffic, maintaining social distancing, facility decontamination, and screening.

The Investigator is responsible for ensuring patient and staff safety, and that study procedures are conducted in accordance with the protocol and Good Clinical Practice (GCP). Any deviations from the protocol that result from the COVID-19 pandemic, and COVID-19-related AEs or SAEs will be documented.

The study team will follow the guidance outlined in their site SOP for managing studies during COVID-19. The risk to patients will be re-evaluated by BPL throughout the COVID-19 pandemic, if deemed necessary by emerging events. BPL's own Risk Management Plan will also provide oversight of the potential impact of COVID-19 on the study.

4.6. Definition of the End of the Study

The end of the study is defined as the final follow-up visit by the last patient. If the sponsor does not choose to trigger an SRC, the study may complete after cohort 1. If the study is terminated prematurely, the study ends when the Sponsor notifies the Investigator in writing that the study has finished, or when the last patient attends the final follow-up visit, whichever is later.

5. SELECTION AND WITHDRAWAL OF PATIENTS

5.1. Number of Patients

Up to twelve evaluable patients with AUD (see [Section 4.2](#)) in up to 2 cohorts (Cohorts 1 and 2)

5.2. Patient Inclusion and Exclusion Criteria

5.2.1. Diagnosis and Main Criteria for Inclusion

To be eligible to participate in this study, patients must meet the following criteria:

1. Willing and able to give informed consent
2. Age 18 to 64 years at Screening
3. Diagnosed with moderate to severe AUD (based on DSM-5)
4. Minimum of 4 HDD in the 28 days before Screening
5. No more than 14 days after the last HDD or completion of detoxification (at point of screening), with no HDD in the 72 hours prior to dosing, and no alcohol at all in the 24 hours prior to dosing
6. Willing to abstain from using recreational drugs from Screening until end of the study
7. Willing to abstain from smoking during their time in the clinic on the day of drug administration as instructed by clinical staff
8. Willing to refrain from psychedelic drug use (excluding the study drug) from Screening until the end of the study
9. Able (in the Investigator's opinion) and willing to undertake and comply with all study requirement, with the ability to complete all protocol-required assessment tools and to comply with all study visits
10. Willing to allow their own general practitioner, and consultant if appropriate, to be informed of study participation
11. Living in stable/secure accommodation in the community
12. In possession of a personal mobile phone and able to nominate at least one locator individual (e.g., a family member, friend, or recovery mentor) with a verifiable address and a telephone number to assist with the arrangement of follow-up appointments

5.2.2. Exclusion Criteria:

